This information will be communicated with the research team via either a custom Epic order set currently in development or a secure online portal developed by the research team. The provider will only have to provide the patient's unique study ID in order to enter this information in the portal. This ID will be securely emailed to the provider upon enrollment of the patient. The provider will be asked to confirm their prescription inputs via the secure online portal to reduce the probability of erroneous data insertion. The provider will also have to confirm the ID of the patient to prevent the provider from erroneously placing a prescription for the wrong patient. No identifying information will be collected by the portal. For participants in the intervention group, this information will be programmed into the digital voice assistant application. For participants in the control group, this information will be recorded for future data analysis.

Intervention group:

Due to the COVID-19 pandemic and the fact that diabetes is a risk factor for the virus, we will mail devices to participants in the intervention group. We will also provide them with the option to set up a phone call or video chat with a member of the research team to help them with device set up.

Device setup will include the following steps:

- Open Alexa Echo Dot package and plug in to power
- Downloading the "Alexa" smartphone application
- Through the Alexa smartphone application, enabling our custom application (called an "Alexa Skill").
- Logging in to our custom application with a unique study ID that is linked to the participant's insulin protocol.

A detailed document called "Alexa Setup Instructions" will be provided to subjects that go into granular detail on how to set up the device as well as its functionalities (screenshots attached).

The entire set up process should take about 5-10 minutes.

Control groups:

For participants in the standard of care control group, we will email them a copy of a blood sugar and medication administration log for them to fill out electronically through REDCap or print and fill out ("Blood Sugar Log"). If a participant doesn't have access to a printer, we will mail them a copy of the log.

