As an additional control, a subset of patients receiving the voice assistant device will also be given a blood sugar and medication administration log and will be asked to use both the voice assistant and the blood sugar and medication administration log for 2 of the 8 weeks they are participating in the trial ("Blood Sugar Log - 2 weeks only")

Data collection:

Data will be collected daily from participants in the intervention and control groups of the study. Participants in the intervention group will be able to interact with our custom app by speaking with their Echo Dot. Participants will be instructed to "check in" with the app once daily at which point the app will collect information about recently checked blood sugars and recent administration of insulin. Data collected by the device will be read back to the patient for confirmation. At the end of the check in, the app will remind patients about the details of their insulin regimen. Based on the patient's self-reported data, this reminder might include a prompt to change the dose of their insulin. All reminders and prompts will be strictly based on the physician-prescribed insulin protocol at the beginning of the study, and prompts will include a summarization of the rationale behind the recommendation (e.g. "Your fasting blood sugars are still above goal. Based on your prescribed treatment plan, you should increase your dose of Lantus to 17 units."). No automated decisions will be made by the voice assistant. The voice assistant will only be assisting the patient with instructions that patients are normally given in writing by their provider.

An instruction manual will be provided to the patient with details on how to interact with the device ("Alexa Setup Instructions"). The only data collected from the patient will be patient-reported blood sugar data and medication administration occurrences. The audio data collected by the device is encrypted and sent to the Amazon cloud for processing into relevant text. The text data is supplied to our application for analysis and storage. Our application will not receive or store any audio data. No protected health information will be collected by our app. All data will be de-identified and stored in the Amazon Web Services cloud. All data will be linked to a participant's unique study ID. A document linking a participant's unique ID to their name and medical record number will be stored on the secure PHI-safe Stanford Medicine Box server.

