Patients in the control group will use their provided log, labeled with their unique study ID, to record their daily blood glucose checks and insulin adherence. This is part of the standard of care in patients with insulin-dependent diabetes. At the end of the trial period, we will collect this log from patients for data analysis. Participants can choose to securely email or upload this log to the research team through REDCap, or if they prefer, they will be provided with a pre-paid envelope to mail the log free of cost.

Finally, user satisfaction survey data will be collected at the beginning and end of the study from patients in the intervention and control groups. The first survey will include "Problem Areas in Diabetes" ("PAID") questions validated in the literature as a rapid screen for diabetes-related emotional distress (<https://pubmed.ncbi.nlm.nih.gov/19841892/>). This survey is labeled "Diabetes Attitudes (PAID) Survey" (screenshots attached). The second survey will include questions specifically tailored towards interrogating the patient's attitude toward and comfort with insulin dose adjustments ("Medication Adherence Survey"). The third and final survey will include questions on attitudes towards healthcare technology ("Health Technology Survey"). All surveys will be collected online via REDCap.

Data analysis:

Members of the research team will review the collected blood sugar and insulin administration data for analysis. Specifically, we will analyze the collected blood sugar data to determine how often blood sugars were checked and how well-controlled they were. We will also analyze insulin administration data to determine how adherent participants were to their prescribed regimen and how effectively participants were able to titrate their insulin to an effective dose. We will also analyze study survey data to assess participant's diabetes selfefficacy and attitudes towards healthcare technology.

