This study poses minimal risk to its participants. Patients in the control group will receive standard of care management of insulin-dependent diabetes. Patients in the intervention arm will not be subject to any risky treatments. They will be interacting with a digital tool that will collect information and remind them of their physician-prescribed treatment plan. The digital tool will not make any autonomous medical decisions or alter the physician's plan in any way. All data collected by the digital tool is anonymized. The voice assistant device will confirm the patient's self-reported data with readback to the subject and verbal confirmation by the subject, prior to storing the data. If a blood sugar reading is outside a standard safe range as determined by their physician, the voice assistant device will provide them the same instructions that would be provided on written instructions by their provider. For example, if a patient's reported blood sugar is less than 70, the voice assistant may notify the subject that their doctor has instructed at such blood sugars to consume something sweet and recheck their sugar. If a patient's reported blood sugar is greater than 350, the voice assistant may notify the patient that their doctor has instructed at such blood sugars to notify a medical professional immediately. If a patient's sugars are dangerously hypoglycemic or dangerously hyperglycemic as determined by their provider, the device will inform the patient to seek medical attention immediately and report to an ER/call 911 per their provider's instructions.

c. Use of Deception in the Study

No deception strategy will be used in this study.

d. Use of Audio and Video Recordings

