4. DEVICES USED IN THE STUDY

a. Investigational Devices (Including Commercial Devices Used Off-Label)

Investigational Device 1	
Name:	Echo Dot
Description:	Voice assistant
Significant Risk?	Non-significant risk
Rationale for Non-Significant Risk	This is a non-significant risk device because it doesn't pose a serious risk to health, safety or welfare of the subject. Its use is not of substantial importance in diagnosing, curing or treating disease.

Investigational Device 2	
Name:	Insulin titration algorithm
Description:	Insulin titration protocol algorithm
Significant Risk?	Non-significant risk
Rationale for Non-Significant Risk	PCPs routinely provide patients with instructions on how to titrate their insulin at home. This algorithm helps patients implement these instructions (which is something they would otherwise be doing with no assistance). We do not believe that the software is more dangerous than standard of care, and is hopefully safer for a few reasons: 1) The provider will be able to set a limit to how much and how often the algorithm will increase the insulin dose. 2) The provider will be able to set a maximum insulin dose. 3) The default insulin titration protocol that we provide mirrors the 2020 consensus statement from AACE (American Association of Clinical Endocrinologists) and ACE (American College of Endocrinology) guidelines (https://pro.aace.com/pdfs/diabetes/algorithm-exec-summary.pdf), but is more conservative to have less tolerance for hypoglycemic events 4) In partnership with Endocrinologists and as Internists ourselves, we have a well thought out, professional guideline-based, conservative hypoglycemia protocol that reduces insulin dose and automatically turns off the titration algorithm if needed to account for various clinical situations where hypoglycemia may be present. The protocol is also designed to account for when providers may have erroneously started too high an insulin dose. Please see our hypoglycemia protocol attached in section 16 for details. 5.) There are multiple steps for confirmation when reporting data to ensure correct data acquisition, including reminders with every single check in that a "fasting blood sugar" is one where one has not had anything to eat in the 8 hours prior

b. IDE-Exempt Devices

N/A

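### Recorded checking, adherence and self-reported titration come from an app check-in in one arm and a self-kept log in the other, so an arm difference mixes behaviour with completeness of recording

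*Protocol*

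**What the plan says.** Protocol section 2a (Data collection) plans daily entry in both arms: "Data will be collected daily from participants in the intervention and control groups of the study". The route differs by arm.

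- **Intervention.** At a once-daily check-in, "the app will collect information about recently checked blood sugars and recent administration of insulin". Section 2b says the device confirms "self-reported data with readback to the subject and verbal confirmation by the subject, prior to storing the data", and section 4a adds: "There are multiple steps for confirmation when reporting data to ensure correct data acquisition".
- **Control.** Participants receive "a blood sugar and medication administration log for them to fill out electronically through REDCap or print and fill out". On return of the log: "At the end of the trial period, we will collect this log from patients for data analysis".

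Section 2a describes the app data as self-report: "The only data collected from the patient will be patient-reported blood sugar data and medication administration occurrences". Under Data analysis, the same section takes checking frequency, glucose control, adherence and success of titration from these records.

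Three elements bear on comparability:

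- A subset of device users is "asked to use both the voice assistant and the blood sugar and medication administration log for 2 of the 8 weeks". Its size, selection and analysis are not given.
- For participants who complete the 8 weeks, the team will take blood sugar, HbA1c and the latest insulin prescription from the medical record. The stated use is to fill gaps in trial data.
- The starting prescription, fasting goal and titration parameters are captured for both arms by the same order set or portal (section 2a, Device setup). The control arm's entries are kept for analysis. Section 2g lets the physician change the regimen through the portal.

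The SAP contains only the sample-size calculation.

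**The concern.** The app is both the intervention and, in one arm only, the measuring instrument. Randomisation balances the patients but not the instrument, which is assigned with the arm.

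This matters little for the first aim in section 1a. Helping patients log is one of the app's purposes, so fuller logging counts towards feasibility. The second aim is the effect on adherence, blood sugar control and time to optimal dose. For that aim, a blank day counted as no check or no dose turns a recording gap into an apparent behaviour gap. The supplied documents give no rule for a day without an entry.

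The direction is not known. A prompted, confirmed check-in may capture more. A log handed in at the end can be completed later, before collection, and so may look fuller than what was done at the time.

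**Working it through.** **1. The plan's own figure.** The SAP gives 32 participants for 84% vs 40%, 80% power, two-sided alpha 0.05. With unpooled variance and 1:1 allocation (assumed; the ratio is not stated):

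n per arm = (1.960 + 0.842)² × (0.84×0.16 + 0.40×0.60) / 0.44² = 15.18, so 16 per arm and 32 in total.

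The figure reproduces and is not disputed here. It supplies the two arm sizes used below: 16 (from 32) and 25 (from the ceiling of 50).

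**2. Recorded gap with identical true behaviour.** The documents give no capture rates or SDs, so these inputs are assumptions. Both arms truly check on 80% of 56 days. One instrument captures 95% of those days and the other 85% or 90%.

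- True days: 56 × 0.80 = 44.8
- Recorded at 95%: 42.6; at 90%: 40.3; at 85%: 38.1
- Gap: 44.8 × 0.05 = 2.24 days, or 44.8 × 0.10 = 4.48 days, in either direction

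**3. Chance that this gap alone reaches p < 0.05.** Two-sample t-test, two-sided 5%, noncentral t with noncentrality gap / (SD × √(2/n)). SD of recorded days assumed to be 8 or 12.

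| Gap (days) | SD (days) | 16 per arm | 25 per arm |
|---|---|---|---|
| 2.24 | 12 | 8.0% | 9.9% |
| 2.24 | 8 | 12.0% | 16.3% |
| 4.48 | 12 | 17.6% | 25.3% |
| 4.48 | 8 | 33.5% | 49.2% |

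The low end is 3 points above the nominal 5%. The high end needs the larger gap, the smaller SD and the larger trial together. The rate rises with sample size because the gap is bias, not noise.

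**4. Glucose.** Days missing at random reduce the number of readings but do not shift their mean, so only selective omission would bias mean glucose. For the SAP's outcome, suppose both arms truly reached 84%. Recording alone would give 40% in the control arm only if 1 − 40/84 = 52% of its controlled participants were missed.

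**5. What the dual-log subset can show.** Over 14 days the same assumed gap is 14 × 0.80 × 0.05 = 0.56 to 14 × 0.80 × 0.10 = 1.12 recorded days. With m device users and an assumed SD of 1.5 to 2 days for the paired app-minus-log difference, the 95% half-width is t(0.975, m−1) × SD / √m:

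- m = 8: 1.25 to 1.67 days
- m = 16: 0.80 to 1.07 days
- m = 25: 0.62 to 0.83 days

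With 8 users the interval is wider than the gap sought. Even with all 25 it does not resolve the smaller gap. The subset is useful as description only.

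**The case against.** The strongest case is that this is a limit on interpretation in a small feasibility study, and that the plan does not rely on these records alone. Both arms self-report with daily entry planned. The log is described as standard of care, so it is the comparator as well as the instrument, and fuller logging is an intended effect. The dual-log subset compares instruments within the same people. The chart gives one source for HbA1c and prescription, and its extraction is not restricted to participants with gaps. The physician's goal and titration parameters give a common reference for judging titration. Section 2g describes the clinical endpoints as blood sugars from standard care. The Blood Sugar Log itself is an attachment not seen here.

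Much of this stands, and it rules out the reading that the plan has no safeguard. What remains is narrower:

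- The dual-log subset contains only app-prompted people for 2 of 8 weeks, so it cannot show how completely unprompted controls log.
- The prescription and parameters show what was ordered, not what was taken.
- The chart data have a stated role as filler only.
- The section 2g sentence does not say that readings come from one source. Section 2a takes them from the app and the log.

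The SAP's silence on HbA1c by arm applies equally to every other outcome, so it is not evidence of a special gap here.

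**Conclusion.** The point holds for recorded checking frequency, adherence and self-reported titration. In these records alone, behaviour and completeness of recording cannot be told apart by arm, and the supplied documents plan no use of the available safeguards to do so. It is a moderate point, worth acting on because the remedy is cheap.

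The size cannot be established from the documents. The 8% to 49% range shows the mechanism on assumed capture rates and SDs; it is not an estimate for this trial.

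A reader might infer two stronger things that the documents do not support. One is that the glycemic control comparison is itself an artefact of recording. Mean glucose is biased only by selective omission, and a loss of 52% of controlled control-arm participants is implausibly large for recording alone. The other is that the bias favours the app. Nothing in the documents fixes its direction.

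**What to change.** 1. **Section 2a, Data analysis.** Report the HbA1c already to be obtained by arm for all completers, as a common-source supporting measure of glucose control and not only as a filler for missing data. Fix the date window in advance and give the number per arm with a value inside it.
2. **Section 2a, dual-log subset.** Choose the subset at random, with its size set in advance. Report app-versus-log agreement on number of checks, glucose values and doses beside the arm comparison, as descriptive.
3. **Accompanying step.** Count days without an entry the same way in both arms, by a written rule. Report the outcomes as recorded checks, self-reported adherence and self-reported titration, naming the instrument for each arm.

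The cost is a little more analysis for at most 50 people, using data already planned. Limits remain. HbA1c follows clinical timing, may not fall near week 8, and shows neither checking nor adherence. Dual-log users are also prompted by the app, so their logs may be fuller than a control's and the agreement may understate the gap between arms.

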In addition to reviewing data collected by our app and REDCap, the research team will also access the medical record of participants who have completed the trial to obtain certain lab results and medication data to help supplement any missing data from the trial. Specifically, the research team will obtain recent blood sugar and Hemoglobin A1c values, as well as the most recent insulin prescription. This will help the research team perform data analysis in cases where trial data are incomplete. Please note that this is only for participants who have been consented, enrolled and have completed the full 8 weeks of the trial.

If participants decide to withdraw from the study, they can do so at any time by contacting [name] at [contact] or [contact]. After study completion, participants will be able to keep their Amazon Echo device for personal use. Their specific login ID will be disabled which will preclude them from using our custom application after study completion. If participants decide to withdraw from the study before completion, they will be asked to return their Amazon Echo device. They will be provided with pre-paid packaging to do so.

Infection control strategies implemented to ensure the safety of the research staff/faculty who will come to campus and to mitigate risks to them and their families:

1. Personnel are trained on the need to stay home and get tested if they have a new cough, fever, difficulty breathing, chills, muscle pain, headache, sore throat, recent loss of taste or smell.
2. All research staff/faculty will follow Stanford's social distancing protocol, which includes:
 - a. Maintaining physical distancing.
 - b. Use of face coverings and eye protection.
 - c. Frequent handwashing and use of hand sanitizer.
3. Researchers and support staff returning to campus will be required to use the Health Check tool to report health status each day.
4. There will be no participant-facing research staff as the informed consent and patient enrollment process will be conducted virtually.

Infection control strategies implemented to ensure the safety of the research participants:

1. All devices will be cleaned prior to being mailed to the participant.
2. Participants will perform self-setup of their device to avoid the need for an in-person visit with research staff.

b. Procedure Risks

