The experiment will terminate after two months of data collection per patient.

e. Data Safety Monitoring Plan (DSMC)

i. Data and/or events subject to review

N/A

ii. Person(s) responsible for Data and Safety Monitoring

N/A

iii. Frequency of DSMB meetings

N/A

iv. Specific triggers or stopping rules

N/A

v. DSMB Reporting

N/A

vi. Will the Protocol Director be the only monitoring entity? (Y/N)

Yes

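### Neither arm has a described way of recording ER visits, 911 calls, admissions or assisted lows, although the device can direct participants to emergency care

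*Protocol*

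**What the plan says.** Protocol 2.b (Procedure Risks) foresees emergencies. At glucose values the provider regards as dangerous, "the device will inform the patient to seek medical attention immediately and report to an ER/call 911 per their provider's instructions". Under 2.a (Device setup), the treating physician specifies these situations for every participant. They are programmed into the device in the intervention arm and kept for later analysis in the control arm. Section 7.a accepts that titrating on misreported glucose could harm a participant, while regarding serious harm from the small dose steps as improbable.

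Protocol 2.a describes four data sources:

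- **App, intervention arm:** "The only data collected from the patient will be patient-reported blood sugar data and medication administration occurrences".
- **Log, control arm** (and a device subset for 2 of the 8 weeks): used "to record their daily blood glucose checks and insulin adherence", and returned at the end of the trial.
- **Three surveys, both arms, start and end:** diabetes-related distress, comfort with insulin dose adjustment, and, last, "The third and final survey will include questions on attitudes towards healthcare technology".
- **Medical record:** "Specifically, the research team will obtain recent blood sugar and Hemoglobin A1c values, as well as the most recent insulin prescription". Access is limited to consented, enrolled participants who have "completed the full 8 weeks of the trial".

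Section 2.g names blood sugars as the clinical endpoints. In 7.e, the item "Data and/or events subject to review" is answered N/A. Section 4.a says of the titration algorithm: "We do not believe that the software is more dangerous than standard of care, and is hopefully safer for a few reasons". The SAP contains only the sample-size justification and plans no safety analysis.

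**The concern.** For a tool that prompts insulin increases, the outcomes that matter most for safety are clinical events: an emergency visit, an admission, or a low from which the participant could not recover alone. The protocol records each physician's criteria for seeking emergency care in both arms, but describes no record of whether such care was sought.

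Glucose entries are a weak substitute. They are self-reported, and someone who is incapacitated or in hospital is poorly placed to log a reading that day. Reporting also differs by arm: a daily check-in with read-back against a log handed in at the end. Events that staff happen to hear about would not be ascertained equally. The risk is that a report with no recorded emergencies is read as reassurance when nobody was asked.

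**Working it through.** **Step 1. Can each described source record an emergency visit, an admission or an assisted low?**

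- App: no. Its content is confined to glucose and insulin administration.
- Control log: none described. Its content is glucose checks and insulin adherence.
- Surveys: none described. The stated topics are distress, comfort with dose adjustment, and technology.
- Medical record: encounters are not among the items listed, and non-completers are not covered.
- Safety monitoring plan (7.e): events for review are N/A.

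**Step 2. What do the glucose data still provide?** Under 2.b, a reported value is read back and confirmed before it is stored. The reading behind a device-issued ER or 911 instruction is therefore in the dataset. Low and high readings exist in both arms and can be compared, imperfectly. Two things are missing: whether the emergency visit happened, and any severe low that was never entered.

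**Step 3. Arm sizes.** Allocation is not stated, so 1:1 is assumed. The SAP's total of 32 is reproduced by the unpooled normal formula for 84% vs 40%, 80% power, two-sided alpha 0.05:

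- n per arm = (1.960 + 0.842)² × [0.84 × 0.16 + 0.40 × 0.60] / 0.44² = 7.849 × 0.3744 / 0.1936 = 15.18, so 16 per arm and 32 in total.

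The ceiling of 50 gives 25 per arm. This concern does not depend on the power calculation; it only sets the range of 16 to 25.

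**Step 4. Reach of the completers-only limit.** The SAP gives no dropout rate. If 50 enroll and 32 finish, 50 − 32 = 18 participants (18/50 = 36%) would have no record review. That group would include anyone who left because of a serious event.

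**Step 5. What would full ascertainment show?** With zero events in n participants, the exact one-sided 95% upper limit is 1 − 0.05^(1/n):

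- n = 16: 1 − 0.05^(1/16) = 17.1%
- n = 25: 1 − 0.05^(1/25) = 11.3%

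The documents give no event rate, so a range is assumed. The chance of at least one event in an arm is 1 − (1 − p)^n:

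| Assumed 8-week rate | n = 16 | n = 25 |
|---|---|---|
| 1% | 15% | 22% |
| 2% | 28% | 40% |
| 5% | 56% | 72% |
| 10% | 82% | 93% |

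Power of Fisher's exact test (two-sided 0.05) at 25 per arm is 2% for 2% vs 10%, 7% for 5% vs 15%, and 37% for 5% vs 25%. Collected events could be described, but a comparison of arms would be close to uninformative.

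**The case against.** Several stronger conclusions are tempting, and the documents do not support them.

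- *A participant could be sent to the ER and the dataset would show nothing.* Not so. The triggering value is confirmed and stored; the gap is what happened next.
- *Safety cannot be checked at all.* Too broad. Low and high readings allow a partial comparison by arm.
- *The trial claims to test that the device is no more dangerous than usual care.* It does not. The statement in 4.a is a belief offered for the non-significant-risk designation, and it rests on design features such as provider-set dose limits and a hypoglycemia protocol. The stated purposes are feasibility, adherence, glucose control, time to optimal dose and self-efficacy.
- *The surveys do not ask about emergencies.* This cannot be asserted. The survey screenshots, intake survey, log and hypoglycemia protocol are attachments not shown, and the survey descriptions need not be exhaustive.

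The best remaining objection is that a trial of this size could not establish comparative safety even with complete data. That is correct, and it limits what the change can deliver. It does not remove the reason to ask, because a count with a stated limit is information, while zero recorded events without ascertainment sets no limit.

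**Conclusion.** The gap stands in a limited form. As far as the visible protocol and SAP go, emergency visits, 911 calls, admissions and assisted lows are not ascertained in either arm, and the record review would miss non-completers even if encounters were added to its list. The planned efficacy analysis is unaffected; any statement about emergencies would lack data.

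Even full ascertainment supports description only. Zero events in an arm would be compatible with a true 8-week rate of up to 17.1% (16 per arm) or 11.3% (25 per arm), one-sided 95%. This assumes equal allocation and follow-up of everyone counted. The finding lapses if an attached form already asks these questions in both arms, including of participants who withdraw.

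**What to change.** If an attached form already collects these events, cite it in the protocol. Otherwise:

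1. Add the same yes/no items, with dates and covering the period since randomization, to the end-of-study REDCap survey in both arms: ER visit or 911 call for low or high glucose; hospital admission; a low needing another person's help.
2. Ask the same items at withdrawal in both arms. The protocol now describes only participant-initiated contact and return of the device, so this contact has to be written in.
3. Add ER and hospital encounters from randomization to week 8 to the record review, for all randomized participants, including withdrawals where consent allows. Keep the direct questions as well, since the chart may miss care given elsewhere.
4. In the SAP, report counts by randomized arm with exact confidence limits and the number ascertained in each arm. Label them descriptive, and state that 16 to 25 per arm cannot support a conclusion of no added danger.

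The cost is a few minutes per participant, one more field in a chart review already planned, and consent wording for record access after withdrawal. The safety statement may become less favorable. No dose, threshold or clinical instruction changes.
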